There are approximately 2,000 new cases of KS diagnosed in the US annually. Prevalence of KS in the US is estimated by SEER to be 29,000. Globocan estimates there are 4,000 cases a year in North America and Europe and estimates that the 5-year prevalence is 13,000. Five year overall survival is 54% for HIV-associated cases and 87% for HIV uninfected cases, so therefore 5-year prevalence underestimates the total prevalence of disease ([Cancer](#)). Many people with KS need intermittent therapy (most often chemotherapy) for life, which can be limited by cumulative toxicities.

In sub-Saharan Africa, KS is one of the most common tumors, in part because the seroprevalence of KSHV, the etiologic agent, ranges from 40-100% (compared to < 5% in the US). Globocan estimates the global incidence is 42,000 cases/year, and 5-year prevalence is 88,000 ([Cancer](#)). At the Uganda Cancer Institute, it is the third most common cancer. About 500 cases a year are treated at this one center alone. The incidence in HIV-positive patients on antiretroviral therapy

in sub-Saharan Africa is ~150:100,000 person-years, which is higher than that of prostate cancer in men in the US. In addition to HIV associated cases, there is a relatively high underlying prevalence of non-HIV associated cases, about 5/100:000 person-years in South Africa – likely there are even more in Uganda, which is similar to chronic lymphocytic leukemia (CLL) or diffuse large cell B cell lymphoma (DLBCL) incidence in the US.

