## 9.2 Sample Size/Accrual Rate

Two participants at minimum and a maximum of 6 participants at each dose level will be treated. Up to 2 participants who do not complete at least one year of follow up for reasons other than toxicity or disease progression may be replaced. Up to twenty patients will be enrolled in the study.

This protocol is designed to meet clinical needs of women and members of minority groups. The planned enrollment report (below) is based on US HIV demographics and previous studies.

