### 9.4 Analysis of Secondary Endpoints

#### 9.4.1 Objective Response Rate (ORR) to NT-I7 in HIV-positive and HIV-negative adults with KS

To preliminarily evaluate the objective response rate of KS to NT-I7 across all dose levels, KS response will be assessed according to modified ACTG criteria. For primary analysis the best response obtained within 12 months of the first dose of NT-I7 will be used, in all participants administered across study doses. Subset analyses for participants by dose level, HIV status, baseline CD4 greater than or less than 200 cells/uL, and history of prior chemotherapy for any subset in which there are at least 6 participants. A more precise estimate of efficacy will occur in a RP2D expansion cohort where dosing will be uniform. An expansion cohort will be included in an amendment.

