#### 9.4.2 Duration of Response, Progression-free Survival, and Overall Survival of HIV-positive and HIV-negative adults with KS Treated with NT-I7

Statistical methods for censored time-to-event data will be used to estimate overall survival, progression-free survival and duration of response along with 95% CI bands. Kaplan Meier survival estimates will be constructed for each of these survival endpoints with 95% CIs, for up to 1 year following initiation of treatment in all participants. Overall survival will be defined as the time from administration of the first dose of NT-I7 until death or censoring, progression free survival will be defined as the time from administration of the first dose of NT-I7 until disease progression or death or censoring, and duration of response will be measured in subjects who obtain a partial response or better and defined as time from the best response within the first 36 weeks of therapy until disease progression or censoring. Subsequently, Cox proportional hazards regression will be used to estimate hazard ratios with 95% CIs for HIV-positive versus HIV-negative participants, adjusted for disease stage.

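### With at most 20 participants, the stage-adjusted Cox hazard ratio for overall survival by HIV status (section 9.4.2) is very unlikely to be estimable, and the plan has no fallback

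*Combined protocol and SAP*

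**What the plan says.** Section 9.4.2 defines OS, PFS and DOR. It plans Kaplan-Meier estimates "for up to 1 year following initiation of treatment in all participants" and then states: "Cox proportional hazards regression will be used to estimate hazard ratios with 95% CIs for HIV-positive versus HIV-negative participants", "adjusted for disease stage". No endpoint is exempted. The section gives no minimum group size, no minimum event count, no time horizon for the Cox model and no fallback if the model fails.

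On size, section 9.2 says: "Up to twenty patients will be enrolled in the study". Section 9.3 rules out stratification, and no quota is set for HIV-negative participants. For mortality, section 2.1.2 gives: "Five year overall survival is 54% for HIV-associated cases and 87% for HIV uninfected cases".

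Section 9.4.1 limits response-rate subsets, HIV status among them, by a size rule: the analysis is done "for any subset in which there are at least 6 participants". The Study Summary repeats that rule for response. Section 9.4.2 has no counterpart.

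**The concern.** A Cox model gives a finite hazard ratio for a two-group factor only if each group has at least one event while members of the other group are still at risk. With no deaths among HIV-negative participants, the HIV-positive to HIV-negative ratio runs to infinity. With none among HIV-positive participants it runs to zero, and with no deaths at all it is undefined. In up to 20 participants, with few HIV-negative participants likely and low mortality in that group, one of these outcomes looks much more probable than a usable estimate.

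At stake is a secondary analysis that often cannot deliver the output it promises. Software commonly still prints a number and a Wald interval at the boundary, and these could be read as an HIV effect.

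**Working it through.** **Sample size.** The plan gives no event count, power or precision for the Cox model. Its one relevant figure is the cap of 20. This agrees with three planned dose levels at the maximum of 6 each, plus the 2 replacements allowed in section 9.2: 3 × 6 + 2 = 20.

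**Inputs**
- 5-year OS of 54% (HIV-associated) and 87% (HIV-uninfected), section 2.1.2.
- HIV split: not fixed. Section 2.1.2 puts HIV-related disease above 80% of US cases, so 16:4 is a natural centre. The range used is 18:2 to 10:10 (HIV-positive:HIV-negative).
- Horizon: 1 year is stated for Kaplan-Meier only. Section 6.6 follows participants for 12 months after the last dose, which after four doses is 27 + 52 = 79 weeks, about 1.5 years. It also ends the active study when the last participant reaches 2 years.
- Assumed: constant hazards and no loss to follow-up. The second favours the plan.

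**Hazards.** −ln(0.54)/5 = 0.1232 and −ln(0.87)/5 = 0.0279 per year. The 1-year death risks are 1 − exp(−0.1232) = 11.6% and 1 − exp(−0.0279) = 2.7%.

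**Probability of a death in both groups** by time T, with n₁ HIV-positive and n₀ HIV-negative: [1 − exp(−0.1232·T·n₁)] × [1 − exp(−0.0279·T·n₀)]. For 16:4 at 1 year this is 0.861 × 0.105 = 0.09.

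| Split (N = 20) | Expected deaths, 1 year | Both groups, 1 year | 1.5 years | 2 years |
|---|---|---|---|---|
| 18:2 | 2.1 | 5% | 8% | 10% |
| 16:4 | 2.0 | 9% | 15% | 20% |
| 14:6 | 1.8 | 13% | 21% | 28% |
| 10:10 | 1.4 | 17% | 29% | 39% |

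The HIV-negative group is the limiting one: at 1 year it has no death in 95%, 90%, 85% and 76% of trials, in the order of the table. Fewer participants make matters worse; 12 split 10:2 gives 4% at 1 year.

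**Adding stage.** In 2,000 simulated trials per scenario, with stage split 50:50 and no stage effect (both assumed), all coefficients of the adjusted model were finite in 7%, 8% and 11% of trials at 1 year for 16:4, 14:6 and 10:10. At 2 years the figures were 17%, 24% and 31%. Without stage, the same simulation gave 10%, 12% and 18%, then 20%, 29% and 40%.

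**Other mortality inputs**
- Section 2.4.1 mentions 40% mortality in HIV clinics, with no time frame. Even if 40% of HIV-positive participants died within 1 year, both groups would have a death in only 11% (16:4) to 24% (10:10) of trials.
- Section 2.1.2 also gives survival in classic KS as 70-80%, with no time frame. Read as 5-year survival of HIV-negative participants (an assumption), the probability is 14-21% at 1 year and 29-43% at 2 years for 16:4. For 10:10 it is 26-36% and 54-70%.
- If HIV-negative participants died at the HIV-positive rate, it is 19% (18:2) to 50% (10:10) at 1 year, and 38% to 84% at 2 years.

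**Precision when a ratio is obtained.** Roughly, SE(log HR) = 1/√(d·a·(1 − a)), with d deaths and HIV-negative share a. For 16:4 at 1 year, d = 1.97 and SE = 1/√(1.97 × 0.2 × 0.8) = 1.78, so the 95% interval reaches a factor of exp(1.96 × 1.78) ≈ 33 either side. For 14:6 and 10:10 the factors are about 24 and 26. In the most favourable case above (equal rates, 10:10, 2 years), d = 4.37 and the factor is still about 6.5.

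**PFS, for contrast.** Section 2.1.4 cites PFS of about 16 months (a first-line median) and about 6 months (relapsed or refractory, treated here as a median). Applied to both HIV groups, 20 × (1 − 2^(−12/16)) = 8.1 and 20 × (1 − 2^(−12/6)) = 15 events are expected by 1 year. For 16:4 to 10:10, both groups have an event in 87% to over 99% of trials, with interval factors of about 2.8 to 5.6.

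**The case against.** The best counter-argument has four parts.

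*Horizon and mortality are not fixed.* This stands. The 1-year limit belongs to the Kaplan-Meier sentence, and the survival figures describe KS cases in general, not trial participants. With longer follow-up and higher HIV-negative mortality, deaths in both groups can become more likely than not. A reader might infer that the OS ratio cannot be estimated at all; the documents do not support that. The result is a probability that depends on assumptions. The ratio would still be extremely imprecise in those favourable cases.

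*The 6-participant rule is not a true parallel.* This largely stands. The rule governs separate response rates in subsets, whereas a Cox term uses everyone. A reader might infer that its absence from section 9.4.2 is the defect, or that adding it would be the cure. It would not: at 14:6, which meets the rule, both groups have a death at 1 year in only 13% of trials. If 20% of participants are HIV-negative, the chance of fewer than 6 among 20 is 80%, so the rule would mostly suppress the contrast.

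*PFS and DOR.* A reader might extend the point to all three endpoints. For PFS the figures point the other way: usually estimable, though imprecise. For DOR the model is confined to responders, so it has fewer participants. Without a response rate in the plan, no probability can be given.

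*Nothing depends on it.* This is true as far as it goes. Objective 1.2.3 does not itself require an HIV contrast, and section 9.4.1 describes its response analysis as preliminary. That limits the importance of the point but does not make the stated analysis workable.

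**Conclusion.** The concern holds for OS as a statement of probability. On the protocol's own 54% and 87%, with constant hazards and 20 participants split 18:2 to 10:10, both HIV groups have a death in 5-17% of trials at 1 year, and in no more than 39% at 2 years. Otherwise, in 83-95% of trials at 1 year and 61-90% at 2 years, the unadjusted OS ratio is zero, infinite or undefined. Stage adjustment makes this worse.

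The conclusion weakens if HIV-negative mortality is well above the 87% figure implies, most of all with an even split and 2 years of follow-up. No documented input makes the ratio informative.

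This is a secondary analysis in a phase 1 trial. Dose escalation and the dose-limiting toxicity and MTD objective do not use it. The change is worth making but is not critical.

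**What to change.** In section 9.4.2:
- Replace the Cox model for OS with Kaplan-Meier curves and numbers of deaths by HIV status.
- Keep Cox for PFS. Keep it for DOR only if both HIV groups have events among responders.
- Where Cox is kept, use Firth-penalised likelihood with profile-likelihood intervals, enter stage as one binary term (for example T0 versus T1, the categories in section 3.1.4), state the time horizon, and label the result descriptive.
- Optionally carry over the 6-per-group rule for consistency with section 9.4.1, without relying on it to rescue OS.

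Penalisation would also give a finite OS ratio. With one or two deaths, however, that value would owe much to the penalty, so counts and curves are the more honest report.

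The cost is a few sentences of text and the loss of a nominal OS hazard ratio that would rarely be interpretable. No data collection, sample size or primary analysis changes.

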#### 9.4.3 Kinetics of CD4+ and CD8+ T cells in blood, and on levels and phenotype within tumors, using flow cytometry and immunohistochemistry, respectively.

It is hypothesized that NT-I7 will lead to T cell expansion over the first 4-8 weeks after administration and that increases will be measurable in the blood using total blood counts with automated differentials and flow cytometry and in tumors by immunohistochemistry at 9 weeks. For blood measurements, ALC will be measured primarily, while absolute CD4+ and CD8+ T cell will be evaluated secondarily. Tumor infiltrating lymphocytes (TILs) will be evaluated quantitatively (cells/hpf) with qualitative annotation of the pattern of distribution.

For analysis of circulating lymphocytes we will first describe fold-change (median and range) in blood ALC from pre-administration to each time point following first administration (1, 4, and 9 weeks), and by category of selected participant characteristics (e.g., dose level, age [by decade], sex, HIV status, prior systemic therapy, and in HIV+, by CD4+ T cells (< versus  $\geq$  200 cells/uL). More formally, we will explore multilevel negative binomial regression to estimate fold-change from pre-administration, adjusted for NT-I7 dose, HIV status, prior therapy, and baseline CD4+ T cell counts. In this analysis, ALC is the dependent variable and a generalized linear mixed model is applied with time from administration (weeks), an indicator of first or second administration, and gap between first and second administration as independent variables of interest in addition to adjustment variables. A random intercept is included for each participant to incorporate correlation between T cell counts from the same participant. The exponentiated fixed-effects model coefficients estimate fold-change from baseline with 95% CIs for a representative participant.

The same analytic approach will be applied to analysis of CD4+ and CD8+ T cells separately, and to TIL counts.

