##### 2.3.2.1 Completed Study of GX-I7-HV-001

A first in human (FIH) Genexine trial (Study No. GX-I7-HV-001) in healthy volunteers was conducted with a single dose of NT-I7 with a dose range of 20 µg/kg (cohort 1, SQ) to 60 µg/kg (cohort 2, SQ; and 60 µg/kg cohort 3, IM). NT-I7 treatment was well tolerated in healthy volunteers after single SC or IM administration. GX-I7-HV-001 was a randomized, double-blind, placebo-controlled, dose-escalation, Phase 1 study to assess safety, tolerability, pharmacokinetics (PK), and pharmacodynamics after a single SC or IM administration of NT-I7 in healthy volunteers. Eligible subjects randomly received NT-I7 or placebo in an 8:2 ratio at one of the following doses: 20 µg/kg SC, 60 µg/kg SC, or 60 µg/kg IM.

NT-I7 was slowly absorbed, particularly after SC administration (time to maximum concentration [ $T_{max}$ ]: 36 to 42 hours postdose) and was slowly removed from the body ( $T_{1/2}$ : 48 to 112 hours), resulting in a flat PK profile, typically seen in biologics. IM NT-I7 was more rapidly absorbed than SC NT-I7 (median  $T_{max}$ : 4 hours vs 36 hours postdose for IM vs SC, respectively), and exposure was ~2 times larger following IM than SC administration at the same

dose of 60  $\mu$ g/kg, although the difference was not statistically significant. The PK parameters of NT-I7 were more variable after IM administration than SC injection. After SC administration, the exposure to IL-7 was increased in a dose-proportional manner. PK parameters are summarized in NT-I7 Investigator's Brochure.

The pharmacodynamics assessments as observed by the ALC was increased in a dose-dependent manner after NT-I7 IM or SC administration (111.4% IM vs 75.1% SC for percent change from baseline at the same dose of 60  $\mu$ g/kg). The increase in ALC peaked approximately 3 weeks after administration of NT-I7, and it lasted over several weeks. An initial 40% to 60% decrease in ALC was seen in all subjects within 4 days after NT-I7 administration was likely due to "homing effect". Pharmacodynamic parameters are summarized in NT-I7 Investigator's Brochure.

[figure not shown]

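### Section 9.4.3: the lymphocyte model's coefficients are not, as stated, all fold-changes from baseline, and without a dose-by-time term the model forces one fold-change on every dose level

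*Combined protocol and SAP*

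**What the plan says.** Section 9.4.3 has two steps. The first is descriptive: median and range of the ALC fold-change "from pre-administration to each time point following first administration (1, 4, and 9 weeks"), overall and by participant characteristics that include dose level.

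The second is a model: "More formally, we will explore multilevel negative binomial regression to estimate fold-change from pre-administration". Dose appears only among its adjustment terms, since the estimate is to be "adjusted for NT-I7 dose, HIV status, prior therapy, and baseline CD4+ T cell counts". The form of the model is given as "a generalized linear mixed model is applied with time from administration (weeks), an indicator of first or second administration". The interval separating those two doses is listed too, with the "gap between first and second administration as independent variables of interest". For the correlation structure, "A random intercept is included for each participant to incorporate correlation between T cell counts from the same participant". The reading of the output is then stated: "The exponentiated fixed-effects model coefficients estimate fold-change from baseline with 95% CIs for a representative participant". The same approach is to be used for CD4+ and CD8+ counts and for tumor-infiltrating lymphocyte (TIL) counts.

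The section does not say whether weeks is numeric or categorical. It names no curved time term and no interaction between dose and time.

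**The concern.** Two features do not fit the stated interpretation.

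**Time.** With a log link, the exponentiated coefficient of a numeric week variable is the ratio of expected counts for one extra week, the same for every week. The protocol expects a different shape. Section 2.3.2.1 reports an ALC fall of 40% to 60% within 4 days, and then: "The increase in ALC peaked approximately 3 weeks after administration of NT-I7". Section 6.2.1 puts the return to baseline at 5 to 7 days. A log-linear trend cannot follow that course.

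**Dose.** Section 2.3.2.2 reports dose-dependent T-cell increases, so a dose effect here means a different fold-change at different doses. An additive dose term can only move the whole curve up or down, including the pre-dose value, on which dose can have no effect. Its coefficient mixes chance baseline differences between cohorts with a diluted drug effect.

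At stake is the only analysis in section 9.4.3 that yields confidence intervals for the T-cell effect. Read as the plan instructs, it would attach the wrong label to most of its estimates and could understate both the expansion and its dependence on dose.

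**Working it through.** The plan gives no sample size, precision or effect figure for this model, so there is none to reproduce. The check is what the coefficients estimate. Least squares on the log scale stands in for the log-link negative binomial fit.

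**Inputs**
- Visits at weeks 0, 1, 4 and 9 after dose 1 (section 9.4.3).
- Week-4 fold of about 2.1: an assumption, taken from the 111.4% rise at 60 µg/kg IM in section 2.3.2.1 (fold 2.114). That dose is far below the 480 to 1200 µg/kg used here.
- Week-1 fold 0.5 to 1.0 and week-9 fold 1.0 to 2.0: assumed ranges, because the documents give no values.
- At most 6 participants per dose level (section 9.2).

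**1. Numeric weeks, one worked profile.** The mean week is 3.5, so the deviations are −3.5, −2.5, 0.5 and 5.5, and the sum of squares is 12.25 + 6.25 + 0.25 + 30.25 = 49. With folds 1, 1, 2.1 and 1.3, the logs are 0, 0, 0.742 and 0.262, and the cross-product is 0.5 × 0.742 + 5.5 × 0.262 = 1.814 (unrounded logs). The slope is 1.814/49 = 0.037 per week. The implied week-4 fold is exp(4 × 0.037) = 1.16, against 2.1 assumed.

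**2. Range over the assumed profiles (week-4 fold 2.114, log 0.749)**

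| Week-1 fold | Week-9 fold | Cross-product | Ratio per week | Implied week-4 fold | Implied week-9 fold |
|---|---|---|---|---|---|
| 1.0 | 1.0 | 0.374 | 1.01 | 1.03 | 1.07 |
| 0.5 | 2.0 | 5.920 | 1.13 | 1.62 | 2.97 |

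The line misses the week-4 value throughout this range. In the second row it also overshoots week 9 (2.97 against 2.0).

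**3. Additive dose, any coding of time.** Assume folds at weeks 0/1/4/9 of 1/0.9/1.5/1.2 at 480 µg/kg, 1/0.9/2.1/1.5 at 960 and 1/0.9/3.0/1.8 at 1200. The 1200-to-480 ratios are 1, 1, 2.0 and 1.5. With balanced visits, the dose coefficient is their geometric mean: exp[(0 + 0 + 0.693 + 0.405)/4] = exp(0.275) = 1.32. It is the same with numeric or categorical weeks.

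For TIL counts with only the mandatory biopsies (baseline and week 9), a true week-9 ratio of 2.0 would appear as √2 = 1.41.

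**4. Categorical weeks without interaction.** The week-4 coefficient is (1.5 × 2.1 × 3.0)^(1/3) = 2.11 and the week-9 coefficient is (1.2 × 1.5 × 1.8)^(1/3) = 1.48. These are genuine fold-changes from baseline, but pooled over doses.

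**5. Categorical weeks with dose interaction.** Without noise, this returns each dose's own folds. The week-4 interaction for 1200 versus 480 is 3.0/1.5 = 2.00, and the dose main effects are 1.00.

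**6. Simulation.** 200 trials used the profiles in step 3, with 6 participants per dose, negative binomial counts (size 16) and random-intercept SD 0.35. They were analyzed with a random-intercept model on log counts; a few fits gave convergence warnings. The additive dose coefficient was significant at 5% in 27.5% of trials. The week-4 interaction (median 1.91, truth 2.0) was significant in 88%.

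**7. Precision of the interaction.** Assume a within-participant SD of 0.25 on the log scale. A change from baseline then has variance 2 × 0.0625 = 0.125. Comparing 6 with 3 participants gives SE √[0.125 × (1/6 + 1/3)] = 0.25, so a ratio of 1.625 has a 95% CI of 1.00 to 2.65. With 6 and 6, the SE is 0.204 and the interval runs from the estimate divided by 1.49 to the estimate times 1.49.

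**The case against.** **The text never says linear.** Weeks may be only the unit, and the preceding sentences name discrete visits. With visit categories, the week coefficients are pooled fold-changes, as the plan says. This stands, and it makes the time half of the point conditional. It does not touch the dose half, nor the fact that the interpretation sentence covers the dose, HIV, prior-therapy, administration and gap coefficients.

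**The model is exploratory and follows a descriptive step.** This also stands. A doubling, or a dose gradient, would show in the medians by visit and dose level. The limitation belongs to the model, not to the whole section.

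**A small model suits a small trial.** Step 7 shows how wide the interaction estimates may be. That argues for labelling them as estimation, not for imposing equal fold-changes.

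Several stronger readings are tempting but unsupported:
- A reader might infer that the model is bound to report almost no expansion. With a week-1 fold of 1.0 and a week-4 fold of 2.1, the implied week-4 fold is 1.16, 1.27 or 1.41 for week-9 folds of 1.3, 1.6 or 2.0. Section 2.3.2.1 says that the rise lasted several weeks.
- A reader might infer that the gap between doses is a constant. Sections 6 and 7 provide for holding doses for a high ALC or HIV viremia, so it can vary.
- A reader might infer that baseline CD4 as a covariate biases the CD4 model. In 100 simulated balanced trials, including it moved the week-4 estimate by less than 1e-14 and left the standard error at 0.101.
- A reader might infer that doses 3 and 4 were overlooked. Section 2.4.1 sets the aim as kinetics after the first two doses, and the Study Calendar has no week-1 or week-4 sample after doses 3 and 4.
- A reader might infer that this model decides the recommended Phase 2 dose. Section 6 defines the maximum effective dose by observed T-cell effects and does not name this regression.

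**Conclusion.** The point holds as a correction to a secondary, exploratory analysis.

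Under any coding of time, the interpretation sentence is wrong for every coefficient that is not a visit contrast, and the absence of a dose-by-time term imposes the same fold-change at all doses. Under the assumed profiles, dose ratios of 2.0 and 1.5 at weeks 4 and 9 shrink to a coefficient of about 1.32: a diluted dose effect, not an absent one.

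If weeks is numeric, which is the plain reading, the time coefficient is also not a fold-change from baseline. An assumed week-4 fold of about 2.1 is then rendered as 1.03 to 1.62.

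These sizes rest on assumed profiles and variances, not on trial data. The structural conclusions do not. The primary objective and the descriptive fold-changes are unaffected.

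**What to change.** Reword the model paragraph of section 9.4.3:
- Enter scheduled visit as a category with pre-dose as reference: 0, 1, 4 and 9 weeks after dose 1, and the visits actually scheduled after dose 2 (weeks 13 and 18, that is, 4 and 9 weeks after it). State that the week-9 pre-dose sample counts once, as 9 weeks after dose 1. The administration indicator is then absorbed by the visit categories. For TIL counts, use the biopsy visits.
- Add a dose-level-by-visit interaction, labelled estimation only.
- Report fold-change as visit-versus-baseline contrasts, by dose level and pooled, with 95% CIs.
- Limit the interpretation sentence to those contrasts. Describe any other coefficients as adjusted ratios.

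No new data or visits are needed. The cost is more parameters: with six blood visits and three dose levels, five visit contrasts and 5 × 2 = 10 interaction terms. With at most 6 participants per dose, the dose-specific intervals will be wide, so the pooled contrasts should be shown beside them. If the sponsor prefers the smaller model, the minimum is to state how time is coded and correct the interpretation sentence.

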### 2.4.1 Risk Benefit Analysis in HIV associated Kaposi Sarcoma

Cancer is the leading cause of death in people with HIV. KS is associated with 40% mortality in HIV clinics in the US and Canada. Scalable T cell modulating therapies with minimal toxicities are highly desirable for KS. Based on the literature to date, the benefits of an effective immunotherapy for KS outweigh the theoretical risk of increasing the HIV reservoir. We hypothesize that NT-I7 will have a favorable therapeutic index in people with KS. Optimizing the dosing schedule will be important in the evaluation of NT-I7 in this patient population. CD4 lymphocytopenia in people living with HIV has a specific etiology and is substantially unique from other cancer populations. KS responses based on changes in CD4 counts have been established in the setting of HIV, distinguishing it from other cancers. The dosing schedule for this proposal is based on PD data from short acting IL-7 in people living with HIV and no cancer (Figure 1). In this study by Thiébaut *et. al.*, participants received weekly IL-7 for 3 weeks, had a peak CD4 count on week 4 that gradually declined over time. The CD4 count at week 4 decreased from peak but remained elevated compared to baseline. NT-I7 (IL-7-Fc) has much longer serum half-life than IL-7. The proposed schedule was suggested by NeoImmuneTech (NIT). NIT has preclinical data showing that over stimulation from too frequent dosing might have a negative effect. At present there does not appear to be a compelling rationale for more frequent dosing in HIV associated cases. This Phase I study will evaluate the kinetics of peripheral and tumor T cell expansion after the first and second doses of NT-I7. Evaluation of the safety of NT-I7 will include stopping rules for clinically significant events related to treatment of HIV (i.e., induction of HIV viremia with a drug resistant strain; clinical AIDS-defining events attributed to HIV viremia and associated immune decline despite demonstration of HIV adherence) as well as detailed evaluation of the effects on the HIV reservoir.

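### Section 9.4.3 does not state the form of time: as a numeric week term it would understate the week-4 lymphocyte rise, and with no time-by-administration interaction it cannot show second-dose kinetics

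*Combined protocol and SAP*

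**What the plan says.** Section 9.4.3 starts from the hypothesis that "NT-I7 will lead to T cell expansion over the first 4-8 weeks after administration". The blood analysis then has two steps.

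- Description: "we will first describe fold-change (median and range) in blood ALC from pre-administration to each time point following first administration (1, 4, and 9 weeks"), also broken down by dose level, HIV status and other characteristics.
- Model: "More formally, we will explore multilevel negative binomial regression to estimate fold-change from pre-administration". ALC is the outcome, each participant has a random intercept, and "a generalized linear mixed model is applied with time from administration (weeks), an indicator of first or second administration", with the gap between the two doses as a further covariate of interest. No visit terms, spline or interaction between time and administration number is listed.

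On interpretation, the section says: "The exponentiated fixed-effects model coefficients estimate fold-change from baseline with 95% CIs for a representative participant". The same approach is to be used for CD4+, CD8+ and TIL counts.

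Three other places bear on this. Section 2.4.1 says the study will "evaluate the kinetics of peripheral and tumor T cell expansion after the first and second doses". Section 2.3.2.1 reports a 40% to 60% fall in ALC within 4 days, and then: "The increase in ALC peaked approximately 3 weeks after administration of NT-I7, and it lasted over several weeks". The note in Section 6.2.1 puts the return to baseline at 5 to 7 days after the first injection.

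**The concern.** The covariate list and the stated interpretation do not fit together on the natural reading. A variable measured in weeks and entered as one number has a coefficient that, exponentiated, is a fold-change per week. It becomes a fold-change from baseline only if time is coded as visits with the pre-dose visit as reference. Two programmers could implement the paragraph differently and both claim to have followed it.

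The choice matters because the expected course is not monotone. A constant weekly trend is a poor summary of a count that dips, recovers, peaks near week 3 and then declines.

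The second-dose question is separate. The administration indicator is a main effect, so the model allows a different average level after dose 2 but the same time profile. It cannot show whether expansion after dose 2 is larger, smaller or absent, although Section 2.4.1 promises kinetics after both doses.

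This is the only model given for secondary objective 1.2.4.

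**Working it through.** The plan gives no power, SD or sample-size figure for this model, so there is no stated number to reproduce. The check asks what a numeric week term would return for plausible profiles.

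**Inputs from the documents.** ALC is sampled at weeks 0, 1, 4, 9 (before dose 2), 13 and 18 (Table 7, Section 5.5). Week 1 is taken as 1.0-fold (Section 6.2.1 note). The rise is 111.4% after one IM dose in healthy volunteers, about 2.1-fold (Section 2.3.2.1). At most 20 participants are enrolled (Section 9.2).

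**Assumptions.** The rise is placed at the week-4 visit. The week-9 level is not given, so a range is used.

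**First-dose slope.** Weeks 0, 1, 4 and 9 have mean 14/4 = 3.5 and deviations −3.5, −2.5, 0.5 and 5.5. The sum of squares is 12.25 + 6.25 + 0.25 + 30.25 = 49. With log fold-change zero at weeks 0 and 1:

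slope = [0.5 × ln(week-4 fold) + 5.5 × ln(week-9 fold)] / 49, and fitted week-4 fold = exp(4 × slope).

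Week 4, where the rise is, has weight 0.5. Week 9 has weight 5.5.

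| True week 4 | Assumed week 9 | Slope (log, per week) | Fitted week-4 fold |
|---|---|---|---|
| 2.1 | 1.0 | 0.371/49 = 0.0076 | 1.03 |
| 2.1 | 1.2 | (0.371 + 1.003)/49 = 0.0280 | 1.12 |
| 2.1 | 1.5 | (0.371 + 2.230)/49 = 0.0531 | 1.24 |
| 2.0 | 2.0 (sustained) | 6 × 0.693/49 = 0.0849 | 1.40 |

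The week-4 rise is understated in every row.

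**Would the interval exclude 1?** This was simulated on the log scale with a 2-fold week-4 rise and an assumed within-participant log SD of 0.25 to 0.50. The table gives the share of runs in which the slope was significantly positive at two-sided 5%.

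| Week 9 | Slope significant |
|---|---|
| 1.0 | 0–3% |
| 1.25 | 33–74% (18 participants) |
| 1.5 | 82–100% (18 participants) |
| 2.0 | about 100% |

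A negative binomial fit with 18 participants gave 1.5% in the first case. With visit indicators, the week-4 coefficient recovered about 2.0 throughout. Its interval excluded 1 in 97–100% of runs with 18 to 20 participants, and in 91–100% with 12.

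**Both doses.** Take a 2-fold rise four weeks after each dose and a return to 1.0 nine weeks after each. Fit a common slope plus the second-dose indicator to all six visits.

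- Week 9 coded as nine weeks after dose 1: times are 0, 1, 4, 9 and then 4, 9. Slope = (0.5 − 2.5) × 0.693 / (49 + 12.5) = −0.0225, or 0.978 per week. The indicator absorbs part of the rise, at 1.27-fold.
- Week 9 coded as time 0 of dose 2: times are 0, 1, 4 and then 0, 4, 9. Slope = (2.333 − 0.333) × 0.693 / (8.667 + 40.667) = 0.0281, or 1.028 per week.

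The assignment of week 9, which the plan does not state, reverses the direction of the trend.

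**The case against.** The strongest reply is that the plan never calls time linear. Weeks are a unit. The paragraph names discrete visits and says its aim is fold-change from before administration, which fits categorical time. That stands: the defect is an unstated form whose natural reading conflicts with the stated interpretation.

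A reader might infer that the trial would test for expansion with almost no power and miss a real doubling. The documents do not support that. The model is exploratory and promises estimates with 95% CIs, with no test, alpha or power. The description at weeks 1, 4 and 9 comes first and would show the first-dose rise. Near-zero detection also needs ALC back at baseline by week 9. Section 2.3.2.1 says the increase lasted several weeks, and this trial's doses are 8 to 20 times the 60 µg/kg behind the 2.1-fold figure. At 1.5-fold or more at week 9, the first-dose slope is usually significant.

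A reader might also infer that the recommended dose would be chosen on a faulty estimate. Section 9.1.1.1 refers to pharmacodynamic responses generally, and Section 6 lets intratumor T-cell levels dominate. Neither names this model. Nor do the documents predict a lost second response: Section 2.3.2.2 reports that antibodies did not appear to affect pharmacodynamic endpoints.

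The second-dose point survives. Section 2.4.1 does not promise a formal comparison of doses, but it does promise kinetics after each. The listed model imposes a common shape, and the descriptive step stops at the first administration.

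**Conclusion.** The point holds as a specification defect in a secondary, exploratory model, and it should be corrected. If time is one numeric term, the coefficients are not the fold-changes the plan says they are. A 2.1-fold week-4 rise would be fitted as about 1.03 to 1.24 for week-9 levels of 1.0 to 1.5, and a sustained 2-fold rise as about 1.40. These figures rest on the numeric reading, week 1 at baseline, and the rise placed at week 4. Whether the interval excludes 1 depends on the week-9 level and the within-participant SD, neither of which the documents give.

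The missing interaction does not depend on those assumptions. As listed, the model cannot describe second-dose kinetics separately, and no other blood analysis in Section 9.4.3 does so.

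**What to change.** In Section 9.4.3, replace the numeric week term and the main-effect administration indicator with one indicator per calendar visit (weeks 0, 1, 4, 9, 13 and 18), with week 0 as reference. The exponentiated coefficients are then fold-changes from baseline, and each dose has its own profile.

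- Report week 4 versus week 0, and week 13 versus both week 0 and week 9.
- State that week 9 is the pre-dose-2 value.
- Do not use the ratio of the 13/9 contrast to the 4/0 contrast alone as evidence of a lost second response. Residual elevation at week 9 biases it downward: with equal 2.1-fold peaks and week 9 at 1.5, it is (2.1/1.5)/2.1 = 0.67.
- Apply the same coding to CD4+ and CD8+ counts. Their week-13 draw appears in Table 3 and the Study Calendar but not in Table 7, and these should be reconciled.
- For TIL counts, use indicators for the biopsy visits.

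For the six-visit ALC model, the cost is five visit coefficients in place of two, with at most 20 participants. The change is to wording only and needs no new data.
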